 A tumor biopsy is required at baseline. Tumor tissue (archival within < 6 months of enrollment or recent acquisition) must be available for correlative studies.

Subjects must consent to allow the acquisition of formalin-fixed paraffin-embedded (FFPE) material (block or unstained slides) by study personnel for performance of correlative tissue studies. Fresh tumor biopsies are required for subsequent time points. [REDACTED]

[REDACTED] tumor biopsy sample during combination therapy is only required for subjects on their first cycle of treatment [REDACTED]

AMG 404 to be administered on [REDACTED] dose is [REDACTED]

fter the end of infusion of AMG 994 if a  $\geq$  grade 2 infusion reaction is not observed. The

 Physical exam is required on days [REDACTED] of each cycle. Height will be measured at screening only. Weight will be measured at screening and each study visit where a physical exam is also performed.

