#### **2.3.1.3       Key Risks**

AMG 994 has not been administered to humans, there is no human or clinical experience with AMG 994. Based on biological mechanism of action, nonclinical toxicity studies of AMG 994, and clinical experience with other CD40 agonists, the key safety risks for AMG 994 include infusion-related reactions (see [Table 2-1](#)).

Systemic CD40 molecules have been associated with higher frequency of adverse events such as CRS, thrombocytopenia and elevations in liver enzymes, however since there is requirement for MSLN binding and CD40 crosslinking for AMG 994 mediated agonism it is unlikely these adverse events will be observed with AMG 994. Overall, the results of the nonclinical safety studies support the initiation of AMG 994 clinical studies.

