**Table 4-1: MSLN Expression in Solid Tumors**

Tumor Type	Patients with MSLN Expression – Positive Disease (%)
Mesothelioma	82
Epithelioid	95
Sarcomatoid	0
Pancreatic adenocarcinoma	85
Epithelial ovarian cancer	70
High-grade serous	75
Endometrioid	69
Mucinous	11
Clear cell	52
NSCLC	57
Adenocarcinoma	64
Squamous	21
SCLC	0
Esophageal cancer	28
Gastric cancer	47
Biliary cancer	
Extrahepatic	95
Intrahepatic	10
Other or unspecified	42
Colorectal cancer	30
Cervical cancer	25
Endometrial cancer	59
Breast cancer	
Triple negative	66
Other	1.6
Unspecified	9

MSLN = mesothelin, NSCLC = nonsmall-cell lung cancer

Study assessments will include measures of safety, tolerability, PK, and pharmacodynamics, immunogenicity, and preliminary anti-tumor activity.

AMG 994 will be administered by [REDACTED] cycle

(on days [REDACTED]) and AMG 404 will be administered by

[REDACTED] cycle. The study will be

conducted in 2 parts: Part 1 – Dose Exploration and Part 2 – Dose Expansion. Part 1 is aimed at evaluating the safety, tolerability, PK, and pharmacodynamics of AMG 994 and AMG 404 combination using sequential and concurrent initiation of dosing: (a) 1 cycle of AMG 994 monotherapy followed by combination of AMG 994 and AMG 404 from cycle 2 onwards and (b) AMG 994 and AMG 404 dosing starting on cycle 1 day 1. The MTD/MTCD of the combination in subjects with locally advanced or metastatic solid tumors will be determined using a Bayesian Logistics Regression Model (BLRM) design. Part 2 will further evaluate the safety of the MTD/MTCD and/or a biologically active dose (eg, recommended phase 2 dose [RP2D]) of the combination in specific tumor types.

[figure not shown]
The dose expansion part of the study (Part 2) will be opened once the MTD/MTCD/RP2D of the combination has been determined in Part 1.

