### **Dose-Limiting Toxicity**

All events will be graded using the CTCAE version 5.0. The occurrence of any of the following events during the first or second DLT evaluation period will be considered a DLT, excluding events clearly related to disease progression or intercurrent illness:

- Any grade 5 event
- Grade 4 neutropenia or thrombocytopenia of any duration
- Grade 3 thrombocytopenia with clinically significant bleeding or lasting > 7 days
- Febrile neutropenia
- Grade 4 anemia
- Grade 3 or 4 non-hematologic toxicity, with the following exceptions:
  - DLT Exemption: Grade 3 nausea/vomiting or diarrhea < 72 hours in the absence of maximal medical therapy
  - DLT Exemption: Grade 3 fatigue < 1 week

- DLT Exemption: Asymptomatic grade 3 electrolyte abnormalities that last < 72 hours, are not clinically complicated, and resolve spontaneously or respond to conventional medical interventions
- DLT Exemption: Grade 3 amylase or lipase elevations, as per CTCAE version 5.0, grade 4 elevations in amylase and lipase are defined as being associated with signs or symptoms of pancreatitis
- DLT Exemption: Other laboratory parameters of grade 3, not considered clinically relevant, and improved to grade  $\leq 2$  within 72 hours.
- Any grade 3 event requiring hospitalization
- Recurrent grade 2 pneumonitis
- Delay in cycle 2 treatment for  $> 14$  days due to an adverse event in the dose escalation portion of the study due to study drug-related toxicity, except for immune-mediated toxicities as outlined in [Table 11-3](#) where a longer timeframe is specified
- Any other event requiring permanent discontinuation of AMG 994 (for example, as specified in [Table 11-4](#), Infusion-Related Reactions)

[figure not shown]
The cumulative adverse event profile will be taken into consideration when making decisions on dose escalation and on any other dose-level or safety review.

Any subject meeting the criteria for Hy's Law case (ie, severe drug-induced liver injury) will be considered a DLT. A Hy's Law case is defined as: AST or ALT values of  $\geq 3 \times$  ULN AND with serum TBL of  $> 2 \times$  ULN without signs of cholestasis and with no other clear alternative reason to explain the observed liver-related laboratory abnormalities (see Section [6.2.3](#) for hepatotoxicity management and Section [11.7](#) for further explanation of Hy's law case and Management of Hepatic Function).

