Clinically or medically significant suspected adverse drug reactions, and serious adverse events considered to be related to study procedures will be followed until resolved or considered stable.

The study may be terminated at any point at the discretion of the sponsor.

The DLT window (ie, DLT-evaluable period) during dose exploration will start on day 1 (start of the administration of the first infusion). The duration of the DLT windows and definition of DLT-evaluable subjects are shown below ([Table 6-2](#)).

All available safety data for subjects who are not DLT evaluable will still be evaluated and considered in DLRT recommendations.

A DLT will be defined as any of the events described above occurring in a subject during the DLT window excluding events clearly related to disease progression or intercurrent illness. The CTCAE version 5.0 (see Section 11.4) will be used to grade adverse events.

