
Grade 3 (prolonged [eg, not rapidly responsive to symptomatic medication and/or brief interruption of infusion]; recurrence of symptoms following initial improvement; hospitalization indicated for clinical sequelae)
 
OR
 
Grade 4 (life-threatening consequences; urgent intervention indicated)
	
Permanently discontinue study drug.
	

• Increase monitoring of vital signs as medically indicated until the subject is deemed medically stable.

• Hospitalization may be indicated.

• Treat per institutional guidelines. Additional appropriate medical therapy may include but is not limited to IV fluids, antihistamines, NSAIDs, acetaminophen, narcotics, oxygen, vasopressors, corticosteroids, and epinephrine. In cases of anaphylaxis, epinephrine should be used immediately.

	
No subsequent dosing

--	--	--	-----------------------------

CTCAE = Common Terminology Criteria for Adverse Events; IV = intravenous; NSAIDS = nonsteroidal anti-inflammatory drugs.

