A best overall response of SD requires an on-study imaging of SD or better no earlier than 7 weeks after cycle 1 day 1; otherwise the best overall response will be not evaluable (NE) unless PD is identified.

Evaluation of overall response details provided in protocol appendix 11.

Change from Baseline

Change from Baseline is the arithmetic difference between post-dose assessments and Baseline value.

Change (absolute) from Baseline = (Post-baseline Value – Baseline Value)

Change (percent) from Baseline = [(Post-baseline Value – Baseline Value)/Baseline Value] x 100

C_{max}

Maximum observed plasma drug concentration.

Dose Limiting Toxicity (DLT)

DLTs are the severe toxicities during the first cycle of cancer therapy. A Dose Limiting Toxicity (DLT) is defined as any AE (meeting the criteria listed in section 6.2.1.5 of protocol) occurring during the first treatment cycle of AMG 994 [REDACTED] where relationship to AMG 404 cannot be ruled out.

The DLT window (DLT-evaluable period) will be the first [REDACTED] of AMG 994 treatment (starting cycle 1, day 1). A subject is evaluable if subject experiences a DLT or completes [REDACTED] of treatment. DLT window will begin from Cycle 2 through study [REDACTED] [REDACTED] for combination of AMG 994 and AMG 404.

Duration of Response (DOR)

The duration of response is defined as time from first evidence of PR or CR to disease progression or death due to any cause. .

DOR will be calculated only for subjects who achieve a confirmed best overall response of PR or better.

DOR (in months) = (Earliest date of disease progression, death, censor - Date of first observation of PR or better + 1)/30.4

Dates of progression and censoring will be determined as described below in table 5.1.

End of Study (End of Trial)

The end of study date is defined as the date when the last subject across all sites is assessed or receives an intervention for evaluation in the study (e.g., last subject last visit), following the final protocol-specified visit (e.g. SFU) or any additional parts in the study (e.g., long-term follow-up, additional antibody testing) whichever is later.

End of Study (Individual Subject)

End of study for each subject is defined as the date the subject last completed a protocol-specified procedure. The date will be recorded on the End of Study CRF page.

End of Study (Primary Completion)

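### The visible SAP definition of a DLT carries an AMG 404 attribution condition that Protocol 6.2.1 does not have, and no change is declared; its exact scope is blacked out

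*SAP*

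**What the plan says.** **Protocol 6.2.1, Dose-Limiting Toxicity.** The rule is broad: "The occurrence of any of the following events during the first or second DLT evaluation period will be considered a DLT". Its one general exception, stated there and repeated at the end of the same section, reads "excluding events clearly related to disease progression or intercurrent illness". No general test of relatedness to either drug applies. One list item, a cycle 2 delay of more than 14 days, does refer to study drug-related toxicity. The list also contains "Any other event requiring permanent discontinuation of AMG 994", with the infusion-related reactions of Table 11-4 as its example.

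**SAP section 5, Dose Limiting Toxicity.** The entry takes over the protocol criteria by reference (to section 6.2.1.5) and ties them to the first treatment cycle of AMG 994. After a blacked-out stretch it adds "where relationship to AMG 404 cannot be ruled out". The same entry later describes a combination window that begins in cycle 2.

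**Use of the definition.** SAP 9.6.1 tabulates early and cumulative DLT incidence by planned dose level and estimates both probabilities with a 2-parameter BLRM. SAP section 10 states that nothing departs from the protocol-specified analyses.

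**The concern.** DLTs are a primary endpoint, and the two documents define them differently. The protocol asks whether a listed event occurred in a window and was not clearly something else. The visible SAP text also asks whether AMG 404 might have contributed. AMG 994 is the first-in-human agent whose dose is being explored and AMG 404 is given at a fixed dose, so a condition naming only AMG 404 could remove toxicity caused by the drug under escalation. Applied as written, it could make the reported cumulative DLT incidence and the final model estimate lower than the protocol definition would give. The only DLT sensitivity analysis, in SAP 9.6.2, relaxes the timing of events and not their attribution, so it would not bring such events back.

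**Working it through.** **1. Which readings fit the rest of the SAP.** SAP 6.3 and 6.4 treat DLTs in the AMG 994 monotherapy cycle as countable, so the clause most plausibly concerns the combination window. Two readings then remain, depending on the hidden words.

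*Reading A: only AMG 404 is named.* Take a subject in a sequential cohort, that is, "1 cycle of AMG 994 monotherapy followed by combination of AMG 994 and AMG 404 from cycle 2 onwards".
- In the first combination cycle, AMG 404 is given after "the end of infusion of AMG 994 if a" grade 2 or higher infusion reaction has not been observed (Protocol Table 1-2 footnotes).
- Suppose a grade 3 infusion reaction occurs during the first cycle 2 infusion of AMG 994. No AMG 404 has yet been given, so a relationship to it is ruled out. This holds whatever happens to AMG 404 later.
- Protocol 6.2.1 counts the event as a grade 3 non-hematologic toxicity; none of the listed exemptions covers it. It also counts through the discontinuation item, because for grade 3 Table 11-4 says "Permanently discontinue study drug".
- The SAP clause would not count it.
- The event type is not far-fetched: Protocol 2.3.1.3 says "the key safety risks for AMG 994 include infusion-related reactions".

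*Reading B: AMG 994 is named as well.* The example then counts. An event judged unrelated to both drugs, yet not clearly due to progression or intercurrent illness, would still be a DLT under the protocol and not under the SAP.

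**2. The plan's own figures.** Protocol 9.2 and SAP 3.2 give the chance of at least 1 DLT at true rates of 10% and 33%, from 1 − (1 − p)^n:
- n = 3: 1 − 0.90³ = 27.1% and 1 − 0.67³ = 69.9% (stated 27% to 70%)
- n = 6: 1 − 0.90⁶ = 46.9% and 1 − 0.67⁶ = 91.0% (stated 47% to 91%)

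These reproduce. The expected number of DLTs in 6 subjects at those rates is 6 × 0.10 = 0.6 to 6 × 0.33 = 1.98, so a single uncounted event is a large part of what will be seen.

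**3. Effect of one dropped event.** The denominator of 6 is illustrative. It is the number of DLT-evaluable subjects that Protocol 4.1 uses in its rules for ending dose exploration. Intervals are exact Clopper-Pearson 95%, the SAP's method for proportions.

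| Counted | Rate | Exact 95% CI |
|---|---|---|
| 2/6 (protocol definition) | 33.3% | 4.3% to 77.7% |
| 1/6 (one event not counted) | 16.7% | 0.4% to 64.1% |
| 1/5 (event not counted, subject no longer evaluable) | 20.0% | 0.5% to 71.6% |

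The last row assumes that the evaluability rule in SAP section 5 (a DLT, or completion of the window) also governs the combination window. The table defining evaluability is not visible.

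**4. What cannot be computed.** The documents give no share of DLTs that the clause would remove. The BLRM shift cannot be calculated because the prior, dose levels and toxicity intervals are blacked out.

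**The case against.** The strongest reply is that half of the key sentence is hidden. The blacked-out words sit directly against the clause, so neither its scope nor the drugs it covers can be known. Under Reading B a cannot-be-ruled-out test is inclusive and overlaps heavily with the protocol's own exclusion. The worked example is one narrow path, and if the evaluability table requires exposure to AMG 404, that rule could remove the subject without help from the clause. The SAP also imports the protocol criteria by reference. Under Sentinel Dosing in Protocol 6.2.1, investigators confirm to the sponsor in writing whether a DLT occurred; if the tables use those calls, nothing is lost. Finally, the SAP is tied to the protocol of 03 December 2020, which is not the version supplied.

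Much of this stands, and it limits the size and certainty of the point. It does not remove the point. The visible clause is an added condition under either reading. The SAP does not say that its tables use the site calls, and the adverse event attributes listed in Protocol Appendix 4 include relatedness but no DLT indicator. The sample serious adverse event form records relationship to each drug separately, so the clause could be applied. On versions, the Amendment 4 rationale mentions no change to the DLT definition, though its list is not exhaustive. The Amendment 1 log, used here for timing only, places the removal of a relatedness criterion in October 2020, before the version that the SAP cites.

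**Conclusion.** The point holds in a modest form. The visible SAP definition adds an attribution condition that Protocol 6.2.1 does not contain, and the SAP declares no change. Under Reading A, at least one kind of event that the protocol names would be missing from the cumulative DLT table and the final BLRM estimate; under Reading B, a relatedness test without basis in the protocol remains. The total effect is unknown, and the halving from 2/6 to 1/6 is an illustration for a single event. All of this assumes that DLTs are derived from the SAP wording.

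Three stronger conclusions are not supported:
- A reader might infer that no event in the AMG 994-only cycle can be a DLT. SAP 6.3 and 6.4 show that such events are meant to count.
- A reader might infer that dose escalation is biased. Protocol 4.1 updates the BLRM for each DLT or suspected DLT, Protocol 6.2.1 has the dose level review team consider all available safety data, and SAP 9.6.2 still tabulates adverse events by grade and relatedness.
- A reader might infer that a large fraction of DLTs would be lost. Nothing in the documents supports any particular fraction.

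**What to change.** Replace the definition in SAP section 5 with: a DLT is any event meeting the Dose-Limiting Toxicity criteria of Protocol 6.2.1 during the first or second DLT evaluation period, "excluding events clearly related to disease progression or intercurrent illness". Then:
- apply that definition to the Early and Cumulative DLT sets and to the BLRM inputs;
- align the sentence that confines DLTs to the first cycle, which conflicts with the SAP's own combination window from cycle 2;
- correct the reference to section 6.2.1.5, a number that the supplied protocol does not contain;
- if an attribution-restricted count is wanted, show it as supplementary and list it in SAP section 10.

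The cost is SAP wording only. No change to data collection, sample size or trial conduct is needed.

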##### **8.2.4.1 Time Period and Frequency for Collecting and Reporting Safety Event Information**

###### **8.2.4.1.1 Adverse Events**

The adverse event grading scale to be used for this study will be the Common Terminology Criteria for Adverse Events (CTCAE) Version 5.0 and is described in Section 11.4.

The investigator is responsible for ensuring that all adverse events observed by the investigator or reported by the subject that occur after first dose of protocol-required therapies through the end of study are reported using the Events CRF.

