###### **8.2.4.1.2 Serious Adverse Events**

The investigator is responsible for ensuring that all serious adverse events observed by the investigator or reported by the subject that occur after signing of the informed consent through end of study visit are reported using the Events CRF.

All serious adverse events will be collected, recorded and reported to the sponsor or designee within 24 hours of the investigator's **awareness** of the event, as indicated in Section 11.4. The investigator will submit any updated serious adverse event data to the sponsor within 24 hours of it being available.

Since the criteria for the CTCAE grading scale differs from the regulatory criteria for serious adverse events, **if adverse events correspond to grade 4 CTCAE toxicity grading scale criteria (eg, laboratory abnormality reported as grade 4 without manifestation of life-threatening status), it will be left to the investigator's judgment to also report these abnormalities as serious adverse events. For any adverse event that applies to this situation, comprehensive documentation of the event's severity must be recorded in the subject medical records.**

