## 11.4 Appendix 4. Safety Events: Definitions and Procedures for Recording, Evaluating, Follow-up and Reporting

### Definition of Adverse Event

Adverse Event Definition

• An adverse event is any untoward medical occurrence in a clinical study subject irrespective of a causal relationship with the study treatment.

• Note: An adverse event can therefore be any unfavorable and unintended sign (including an abnormal laboratory finding), symptom, or disease (new or exacerbated) temporally associated with the use of a treatment, combination product, medical device or procedure.

• Note: Treatment-emergent adverse events will be defined in the SAP.

Events Meeting the Adverse Event Definition

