

• Any abnormal laboratory test results (hematology, clinical chemistry, or urinalysis) or other safety assessments (eg, electrocardiogram, radiological scans, vital signs measurements), including those that worsen from baseline, that are considered clinically significant in the medical and scientific judgment of the investigator (ie, not related to progression of underlying disease).

• Exacerbation of a chronic or intermittent pre-existing condition including either an increase in frequency and/or intensity of the condition.

• New conditions detected or diagnosed after study treatment administration even though it may have been present before the start of the study.

• Signs, symptoms, or the clinical sequelae of a suspected drug-drug interaction.

• Signs, symptoms, or the clinical sequelae of a suspected overdose of either study treatment or a concomitant medication. Overdose per se will not be reported as an adverse event/serious adverse event unless it is an intentional overdose taken with possible suicidal/self-harming intent. Such overdoses are to be reported regardless of sequelae.

• For situations when an adverse event or serious adverse event is due to advanced solid tumors, report all known signs and symptoms. Death due to disease progression in the absence of signs and symptoms should be reported as the primary tumor type (eg, metastatic pancreatic cancer). Note: The term "disease progression" should not be used to describe the adverse event.

• "Lack of efficacy" or "failure of expected pharmacological action" per se will not be reported as an adverse event or serious adverse event. Such instances will be captured in the efficacy assessments. However, the signs, symptoms, and/or clinical sequelae resulting from lack of efficacy will be reported as adverse event or serious adverse event if they fulfill the definition of an adverse event or serious adverse event.

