**Recording Adverse Events and Serious Adverse Events****Adverse Event and Serious Adverse Event Recording**

- When an adverse event or serious adverse event occurs, it is the responsibility of the investigator to review all documentation (eg, hospital progress notes, laboratory, and diagnostics reports) related to the event.
- The investigator will then record all relevant adverse event/serious adverse event information in the Event case report form (CRF).
- The investigator must assign the following adverse event attributes:
  - Adverse event diagnosis or syndrome(s), if known (if not known, signs or symptoms);
  - Dates of onset and resolution (if resolved);
  - Did the event start prior to first dose of investigational product, other protocol-required therapies;
  - Assessment of seriousness;
  - Severity (or toxicity defined below);
  - Assessment of relatedness to investigational product or other protocol-required therapies and/or study-mandated activity and/or procedures;
  - Action taken; and
  - Outcome of event.

- If the severity of an adverse event changes from the date of onset to the date of resolution, record as a single event with the worst severity on the Event CRF.
- It is not acceptable for the investigator to send photocopies of the subject's medical records to sponsor in lieu of completion of the Event CRF page.
- If specifically requested, the investigator may need to provide additional follow-up information, such as discharge summaries, medical records, or extracts from the medical records. In this case, all subject identifiers, with the exception of the subject number, will be blinded on the copies of the medical records before submission to Amgen.
- The investigator will attempt to establish a diagnosis of the event based on signs, symptoms, and/or other clinical information. In such cases, the diagnosis (not the individual signs/symptoms) will be documented as the adverse event/serious adverse event.

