Subjects who are alive and have not progressed, whether on-study or lost to follow-up, will be censored at their last evaluable tumor assessment date. Censoring rules for progression-free survival analysis are given below in Table 5-1.

Safety Follow-Up (SFU)

A safety follow-up visit will be performed approximately 30 (+7) days and 140 days (\pm 1 week) days after the end of the last dose of AMG 994 and AMG 404 combination therapy.

Serious Adverse Event

A Serious Adverse Event is defined as any untoward medical occurrence that, meets at least 1 of the following serious criteria:

- Results in death (fatal)
- Immediately life-threatening
- Requires in-patient hospitalization or prolongation of existing hospitalization
- Results in persistent or significant disability/incapacity
- Other medically important serious event
- Is a congenital anomaly/birth defect

Study Day

Post study day: study day= (date - date of Study Day 1) + 1

Pre-study day: study day= (date – date of Study Day 1)

Study Day 1

It is defined as the first day that investigational product is administered to the subject. The day before Day 1 is referenced as Day -1.

Treatment-emergent Adverse Event (TEAE)

A treatment-emergent adverse event is any adverse event starting on or after the first administration of any study drug, as determined by the flag indicating if the adverse event started prior to the first dose on the Events CRF, and 140 days (\pm 1 week) after the last dose of AMG 994 or AMG 404 whichever is later. The severity of each adverse event will be graded using the CTCAE version 5.0. Adverse events will be coded using MedDRA v23.0 or later.

Treatment-emergent Treatment-related Adverse Event

A treatment-emergent treatment-related AE is any treatment-emergent AE that per investigator review has a reasonable possibility of being caused by the investigational product.

Time to Progression (TTP)

Time to progression is defined as time from the start of treatment until the disease starts to get worse or spread to other parts of the body.

$$\text{TTP (in months)} = (\text{Earliest date of disease progression, censor} - \text{Date of first dose} + 1)/30.4$$

Table 5-2. Censoring Rules for TTP

Situation	Date of Event or Censoring	Outcome
PD, no prior new anticancer therapy or prior to start of new anticancer therapy	PD	Event
No PD, no new anticancer treatment	Last visit; otherwise, first IP dose date	Censored

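### The SAP's treatment-emergent definition has no worsening clause, so an acute serious event that begins in screening and worsens or becomes fatal after first dose can drop out of the treatment-emergent tables

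*SAP*

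**What the plan says.** Protocol Section 11.4 leaves the definition to the analysis plan: "Treatment-emergent adverse events will be defined in the SAP". SAP Section 5 supplies it: "A treatment-emergent adverse event is any adverse event starting on or after the first administration of any study drug", settled "as determined by the flag indicating if the adverse event started prior to the first dose on the Events CRF". The same section makes treatment-related events a subset of treatment-emergent ones.

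Two collection rules apply. Under Protocol 8.2.4.1.2 the investigator reports "all serious adverse events observed by the investigator or reported by the subject that occur after signing of the informed consent". Under Protocol 8.2.4.1.1 adverse events in general are those "that occur after first dose of protocol-required therapies through the end of study are reported using the Events CRF".

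Two passages in Protocol Section 11.4 govern recording. If severity changes between onset and resolution, the site must "record as a single event with the worst severity on the Event CRF". The list of occurrences that qualify as adverse events includes "Exacerbation of a chronic or intermittent pre-existing condition including either an increase in frequency and/or intensity of the condition".

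SAP 9.6.2 then summarises treatment-emergent events overall, at grade 3 or higher, serious, leading to interruption or withdrawal, and fatal, with a parallel set for treatment-related events.

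**The concern.** Each rule is ordinary by itself. The difficulty lies in the combination. A serious event from the screening period is already on the Events CRF with its pre-dose flag set. If it worsens or becomes fatal on treatment, the single-record rule raises the grade but leaves the onset and the flag alone. The SAP looks only at the flag.

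Treatment-emergent events, including grade 3 or higher, serious and fatal ones, are among the primary endpoints (Protocol Section 3, SAP 2.1). An event can be missed this way but not wrongly added, and the events concerned are by construction serious. Where the protocol's exacerbation wording can be read to allow a new record, two sites could code the same clinical course differently, and only one version would reach the tables.

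**Working it through.** The plan states no figure on this point, so there is nothing to reproduce. The check is to follow one case through the rules. Take, purely as an illustration, an acute serious event of grade 3 with onset on study day -5, ongoing at first dose, and grade 5 on day 12.

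1. **Is it collected?** Yes. Day -5 falls within the screening window of up to 28 days (Protocol 8.1.1), and serious events are reported from consent (8.2.4.1.2).
2. **What does the record look like after day 12?** It is one record, with onset on day -5 and worst grade 5 (Protocol 11.4). The CRF item asking whether the event began before first dose stays at yes. The recording rule does not ask for the date on which the grade rose.
3. **Is it treatment-emergent?** No. SAP Section 5 decides by the flag. The start-date imputation in SAP Appendix A makes no difference, because an imputed date does not override the flag.
4. **Which summaries lose it?** The overall, grade 3 or higher, serious and fatal treatment-emergent rows of SAP 9.6.2. The interruption and withdrawal rows lose it too if it had that consequence. If judged related, it also fails the Section 5 definition of a treatment-related event.

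Two variations show the limits:

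- **Non-serious condition before dosing.** It is not collected as an adverse event before first dose. It belongs in medical history, which runs through start of treatment with the current grade of each unresolved condition (Protocol 8.2.1.3). A later worsening can enter as a new event with post-dose onset and so counts. The gap is therefore essentially confined to serious events.
- **Chronic or intermittent condition.** The exacerbation wording in Section 11.4 can support a new post-dose record, which would count. An acute event already open as a record does not clearly fall under that wording, and the single-record rule applies to it directly. Neither document says which rule prevails where both could apply.

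One further comparison: Protocol 9.4.2.3.2 plans tables of fatal and serious adverse events without limiting them to treatment-emergent ones. The corresponding rows of SAP 9.6.2 are limited to treatment-emergent or treatment-related events, while SAP Section 10 declares no changes from the protocol.

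**The case against.** The strongest reply is that exclusion is neither certain nor common. A site that follows the exacerbation wording can open a new record, and in these tumour types a condition such as a pleural effusion might well be treated that way. The course also requires a subject with an ongoing serious event to be dosed at all. The protocol filters such subjects through life expectancy above 3 months (criterion 103), active infection needing therapy (215), other disorders posing a risk (226), and review of safety assessments before each administration (8.1.2). This stands as a limit on frequency and certainty. It does not close the gap for acute events, and it shows that handling can vary by site.

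A reader might infer that such an event escapes safety oversight. The documents do not support that. It is reported to the sponsor within 24 hours, dose level reviews use all available data, and the death counts in overall survival. Neither the dose-limiting toxicity criteria in Protocol 6.2.1 nor the grade 5 accrual suspension in Protocol 9.4.1.1 is worded in terms of treatment-emergent events. The fatal and serious tables in Protocol 9.4.2.3.2 are unrestricted.

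A reader might also infer that the expansion stopping rule is compromised. SAP 7.1 counts treatment-related events of grade 4 or higher, but does not say whether the Section 5 definition applies there. One missed event could matter only if it does, so this remains a question to settle and not a demonstrated failure.

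**Conclusion.** The gap is real and narrow. As written, an acute serious event with onset in screening that worsens or becomes fatal after first dose can be omitted from the treatment-emergent summaries, including the serious and fatal rows, and from related events as SAP Section 5 defines them. This follows from reading the collection, recording and classification rules together. It rests on the assumption that sites apply the single-record rule to such events.

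It would go too far to say that every pre-dose serious event that worsens is excluded, or that the course traced above is typical. The exacerbation wording leaves room for a new record in some cases, and neither document gives any rate for such events. The number of affected subjects cannot be estimated from the documents; given the eligibility filters it is probably small. The direction is clear: undercounting only. The consequence is misclassification in descriptive tables, in a study without hypothesis tests, so this is a low-priority correction.

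**What to change.** (a) At the next protocol amendment, revise the single-record rule in Section 11.4 and reconcile it with the exacerbation wording there. An event with pre-dose onset that increases in grade or becomes fatal on or after first dose should receive a new Event record, or a dated grade change, at the date of worsening.

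(b) State in SAP Section 5 that such worsening is a treatment-emergent event, counted once per subject and preferred term. A SAP clause alone would not work, because a single worst-grade record carries no worsening date. The counting rule is needed so that the original record and the worsening record are not both counted.

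(c) For records already collected, or if the CRF is not changed, classify events with pre-dose onset and a fatal outcome after first dose as fatal treatment-emergent events using the death date. List all serious events with pre-dose onset that were ongoing at first dose.

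The cost is a small change to the protocol and to CRF completion. Because an amendment must go to the ethics committees, it should ride with the next one and not prompt its own. Treatment-emergent counts may rise slightly.
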